including assistance in making produce displays visible and attractive and in hosting in-store events, like taste testings. Our team partnered with the Health Department to evaluate the program. In analyses of sales in 5 intervention and 2 control stores, we detected significant changes in store sales, with intervention stores experiencing a greater increase in fruit/vegetable transactions (146% vs. 11%, p=0.01) and a marginally greater increase fruit/vegetable sales (155% in program stores vs. 22% in control, p=0.057) between baseline (weeks 1-4) and follow-up (weeks 11-14).

III. Specific Aims of the Study

Aim 1: Assess changes in small and non-traditional, urban food stores from baseline to 4-, 12- and 24-months post-policy implementation.

Objective store assessments of healthy and unhealthy food availability, promotion, advertising, quality, price, and placement will allow us to assess the degree of policy implementation, as well as changes in other environmental outcomes not directly specified by the policy. To identify barriers and facilitators associated with implementation, we will also examine patterns of compliance over time (such as "early compliers" vs. "late compliers") and store- and neighborhood-level predictors of these patterns. Our primary hypothesis is that the new policy will result in an increase in healthy food availability in Minneapolis stores at 4-, 12- and 24-months post-implementation, compared to stores in St. Paul, where no policy exists, and that differences in intervention vs. control stores will continue to increase over 24 months.

Aim 2: Assess changes in the nutritional quality of consumer purchases, including assessment of calories and energy density, at small and non-traditional, urban food stores.

We will conduct customer intercept surveys at small and non-traditional stores and assess purchasing via direct observation (i.e., "bag checks"). Our primary hypothesis is that, controlling for any baseline differences, energy density and calories purchased in Minneapolis stores at 4-, 12- and 24-months post-policy implementation will be less than in stores in St. Paul, our control community.

Aim 3: Assess changes in home food availability among households that frequently shop at small and non-traditional, urban food stores.

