The study design is a 2 (Condition: ordinance, no ordinance) X 4 (Time: Baseline, 4-, 12-, 24month) quasi-experimental study. The primary hypothesis will be tested using traditional repeated measures modeling as well as growth curve modeling. The unit of analysis is the store, with Time a within-subjects factor and Condition a between-subjects factor. Condition, Time, and their interaction are modeled as fixed effects. The overall test of any difference by policy condition over time is the Time x Condition interaction, a 3 degree of freedom test. Planned contrasts will be used to examine specific hypotheses using single degree of freedom tests, assessing effects at 4-, 12- and 24-month follow-up. Because stores are not randomized to Condition, the statistical models will include a number of potential store-level covariates as additional fixed effects that have been identified from previous work. Covariance pattern modeling implemented by mixed model regression will be used to estimate the repeated measures model; this model allows residuals to correlate to account for the same stores being measured over time.

The repeated measures general linear mixed model includes time as a fixed effect and examines the effect of the policy on the outcome using the Time x Condition interaction. Using a series of planned contrasts, the effects of the intervention at each time point can be estimated (e.g., baseline to 4 months, baseline to 12 months, etc.). This model does not, however, explicitly model change over time. To examine change over time and how this relates to condition, we will augment these analyses with a series of conditional, multilevel models of change (i.e., growth curve models). These models examine inter-individual differences in intra-individual change by fitting a trajectory, with an intercept and slope, to each store. The intercept and slope can be regressed on predictors and covariates of interest.

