We will test Aim 1 (to assess changes in food availability pre- vs. post-policy implementation, as well as changes in food price, quality, promotion, and placement) by regressing each outcome variable separately on Time, Condition, and the Time x Condition interaction, as well as a number of potential covariates (store characteristics [e.g., type of store, size, customer base, store owner characteristics] and neighborhood characteristics [e.g., race/ethnicity, household income, poverty, education, employment]). The 3 df Time x Condition interaction is the overall test of the hypothesis; we hypothesize that this estimate will be significantly different from zero. We will conduct a set of single df planned contrasts to isolate effects. Controlling for any baseline differences, we will test differences between Condition (Policy vs. no Policy) at 4-, 12-, and 24-months post policy change. We hypothesize that stores in Minneapolis will show significantly

higher healthy food availability scores at all 3 time points. We will supplement these analyses using growth curve modeling. We will fit individual lines to each store's 4 waves of healthy food availability scores, and regress these intercepts and slopes on Condition and the potential covariates. We hypothesize stores in Minneapolis will show no baseline differences and have significantly larger positive slopes for healthy food availability outcomes over time. We will use growth mixture modeling⁽³⁴⁾ to examine policy compliance. Growth mixture modeling relaxes the assumption of population homogeneity and tests the presence of heterogeneity in trajectories. These models will identify subgroups of stores that exhibit similar compliance trajectories over time. After determining the optimal number of mixtures (subgroups), we will regress mixture on Condition (Minneapolis vs. St. Paul) and covariates. It is hypothesized that there will be a number of subgroups (e.g., immediate compliers, delayed compliers, non-compliers), Minneapolis stores will be more likely to be in a compliant subgroup (vs. a noncompliant subgroup), and various store and neighborhood characteristics will be associated with subgroup.

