Because this is a study of a natural experiment, the number of available stores is not controllable. Based on estimates using our inclusion criteria, we expect to have 208 stores at baseline. Using means and variances from a recent study evaluating effects of WIC revisions on HFS scores⁽³⁷⁾ and setting alpha=0.05 (two-tailed) and power=0.80, we will be able to detect a difference in HFS score of approximately 2.2 points at any one time point. This is approximately 0.4 SD units and is much less than the difference found by Andreyeva and colleagues of approximately 4 points on the HFS score.⁽³⁷⁾ Even with substantially smaller sample sizes (i.e., <120 stores), we would have sufficient power to detect effect sizes on this order. Factoring in 20% attrition, the detectable effect increases

to approximately 2.4 units. Actual detectable effects will be much smaller given the additional power due to having multiple rounds of data and including covariates. Sample size calculations were also estimated for aims 2 and 3, also setting alpha=0.05 (two-tailed), and power=0.80. For aim 2, using variance estimates from Borradaile et al,⁽²⁸⁾ 424 intercept surveys at four rounds will allow us to detect a 50-calorie difference (a very small effect size) between conditions over time. For aim 3, 68 households will allow us to detect a 3-point difference (a small effect size) in fruit and vegetable availability and a 4-point difference in obesogenic home food score (also a small effect; variance estimates from Fulkerson et al⁽³⁸⁾, factoring in 20% attrition.

Quality Control

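### Neighborhood predictors of store compliance are to be tested with no allowance for stores sharing a neighborhood, so their standard errors will be too small if such stores are correlated

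*Combined protocol and SAP*

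**What the plan says.** Section III, Aim 1, sets out to examine patterns of compliance over time and "store- and neighborhood-level predictors of these patterns". Section VI (Analyses That Will Be Performed) gives the models:

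- **Unit of analysis.** "The unit of analysis is the store, with Time a within-subjects factor and Condition a between-subjects factor".
- **Repeated-measures model.** The only correlation described is within a store: "this model allows residuals to correlate to account for the same stores being measured over time".
- **Growth curve model.** It works by "fitting a trajectory, with an intercept and slope, to each store". The intercepts and slopes are then regressed on Condition and the covariates.
- **Covariates.** In general terms, "the statistical models will include a number of potential store-level covariates as additional fixed effects". The Aim 1 paragraph then adds area variables to the store characteristics: "neighborhood characteristics [e.g., race/ethnicity, household income, poverty, education, employment".
- **Compliance step.** Growth mixture models, run in MPlus, sort stores into subgroups. Subgroup is regressed on Condition and covariates, with the hypothesis that "various store and neighborhood characteristics will be associated with subgroup".

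No neighborhood random effect, clustered variance or spatial correlation is described. The documents do not define a neighborhood, say how its values are attached to stores, or give the number of stores per neighborhood.

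**The concern.** Area income, poverty or racial composition is normally measured for an area, and every store assigned to that area then carries the same value. For such a predictor, two stores in one area are not two independent pieces of information if they also resemble each other in ways the model leaves out. A model that treats them as independent counts too much information, and its intervals for the neighborhood coefficients are too narrow.

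The documents give some reason to expect such resemblance. Section II (Preliminary Studies) describes a Minneapolis corner store program aimed at at-risk areas (9 stores in 2010, 30 in 2012), supported partly through neighborhood organizations. The store exclusions in Section IV do not name its participants, and program participation is not among the listed covariates.

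At stake is a stated part of Aim 1: which characteristics go with early, late or absent compliance. A false neighborhood association could misdirect implementation support.

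**Working it through.** **The plan's own figure.** Section VI (Sample Size Considerations) says "we expect to have 208 stores at baseline" and gives a detectable difference of about 2.2 points, or about 0.4 SD, at two-sided alpha 0.05 and power 0.80. The split by city is not given, so 104 per city is assumed.

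- Detectable effect = (1.960 + 0.842) x sqrt(2/104) = 0.389 SD, which rounds to 0.4.
- The stated ratio implies an SD of about 2.2/0.4 = 5.5, and 0.389 x 5.5 = 2.14 points.
- After 20% attrition (166 stores): (1.960 + 0.842) x sqrt(2/83) = 0.435 SD, and 0.435 x 5.5 = 2.39 points, against the stated 2.4.

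The figure reproduces to rounding. It concerns the difference between conditions, not neighborhood predictors.

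**Inputs for the neighborhood coefficients.** Stores per neighborhood (m) and the residual ICC after covariates are not in the documents. The ranges below are assumptions: m from 2 to 4, ICC from 0.05 to 0.20.

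**Formulas**, for a predictor constant within neighborhoods of equal size:

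- Design effect DE = 1 + (m - 1) x ICC.
- True SE / model SE = sqrt(DE).
- Model SE too small by 1 - 1/sqrt(DE).
- Actual error of a nominal 5% test = 2 x [1 - Phi(1.96/sqrt(DE))].

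| m | ICC | DE | True/model SE | Model SE too small by | Actual error |
|---|---|---|---|---|---|
| any | 0 | 1.00 | 1.000 | 0% | 5.0% |
| 1 | any | 1.00 | 1.000 | 0% | 5.0% |
| 2 | 0.05 | 1.05 | 1.025 | 2.4% | 5.6% |
| 3 | 0.10 | 1.20 | 1.095 | 8.7% | 7.4% |
| 3 | 0.20 | 1.40 | 1.183 | 15.5% | 9.8% |
| 4 | 0.20 | 1.60 | 1.265 | 20.9% | 12.1% |

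The fourth and fifth columns are different quantities. At m = 4 and ICC 0.20 the true SE is 26% larger than the model SE, which means the model SE is 21% too small.

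**Check by simulation.** Ordinary regressions on 208 stores with a neighborhood-constant predictor of no effect, 4,000 runs each, rejected at a nominal 5% in 5.9% of runs (m = 2, ICC 0.05), 9.2% (m = 4, ICC 0.10) and 12.0% (m = 4, ICC 0.20). With ICC 0 the rate was between 4.7% and 5.1%. With larger areas the problem grows: 14.4% at m = 8 and ICC 0.10.

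The formula and the simulation are for a linear outcome. For the regression of subgroup, which is categorical, they indicate size only.

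**The primary test.** Suppose a store's score contains a neighborhood term that does not change over time. That term appears at baseline and at follow-up and largely cancels from a within-store change. Only a neighborhood term that differs by time would carry into Time x Condition. The documents give no figure for one.

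**The case against.** The strongest reply is that the size of the problem is unknown and may be nil. The documents do not say that stores share neighborhood values. If neighborhoods were drawn as buffers around each store, values would overlap rather than coincide, and the design-effect formula would not apply directly. The relevant ICC is what remains after store type, size, customer base and five area variables are adjusted for, and it could be close to zero. At the low end of the assumed range the error rate is 5.6%, which would matter little. All of this stands, and it makes the bias conditional.

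It is also fair to say that the covariate list in the Aim 1 paragraph serves as adjustment in a model whose test is Time x Condition. A reader might infer from that list alone that the main analysis tests neighborhood coefficients. It does not. They are interpreted in the compliance analysis, through the subgroup hypothesis and the Aim 1 statement on predictors. That analysis supplements the primary hypothesis and names no particular predictor or direction.

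None of this supplies the missing provision. The plan commits to testing neighborhood predictors and describes no method that would protect those tests if nearby stores are alike. Leaving the neighborhood undefined does not help, because the variables cannot be attached to stores until some unit is chosen.

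**Conclusion.** The point holds conditionally. As written, the analysis understates the uncertainty of neighborhood coefficients whenever stores share a neighborhood value and residual correlation is positive. Under the assumed ranges the effect runs from negligible to moderate. Larger areas or stronger correlation would make it worse.

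Two stronger conclusions are tempting, and the documents do not support them. One is that the policy effect itself is reported with too much certainty: that would need change over time to be correlated within neighborhoods, for which there is no evidence or figure. The other is that the sample size is wrong: the stated detectable differences reproduce and do not rest on the neighborhood coefficients. The point is worth acting on because it concerns a stated Aim 1 inference and is cheap to settle, not because it threatens the primary result.

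**What to change.** 1. Define the neighborhood unit, say how its values are attached to stores, and report the number of stores per unit. If store-centered buffers are used, say how correlation between overlapping buffers is handled.
2. In the compliance-subgroup regression, use neighborhood-clustered standard errors through a cluster option in MPlus. A change to the SAS models would not reach this step.
3. Where neighborhood coefficients are interpreted in the SAS MIXED repeated-measures model, add a neighborhood random intercept or use neighborhood-clustered standard errors.
4. In the growth model, allow slopes to cluster by neighborhood where this can be estimated, and otherwise use clustered standard errors. With few stores per area, a neighborhood-by-time variance may be poorly estimated or fall at zero, so the fallback should be written down in advance.

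No new data are needed beyond assigning each store to a unit, which the neighborhood covariates already require. The cost is a little more analysis work and slightly wider intervals for neighborhood predictors. If the ICC proves close to zero, the results will barely change.

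### If the ordinance acts early, the Aim 1 growth curve's straight line records part of its effect as a baseline difference between the cities

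*Combined protocol and SAP*

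**What the plan says.** Section VI, Analyses That Will Be Performed, describes the design as a "2 (Condition: ordinance, no ordinance) X 4 (Time: Baseline, 4-, 12-, 24month) quasi-experimental study", so one wave is pre-policy and three are post-policy. It defines the growth curve as "fitting a trajectory, with an intercept and slope, to each store". For Aim 1 it says: "We will fit individual lines to each store's 4 waves of healthy food availability scores, and regress these intercepts and slopes on Condition" and the covariates. The hypothesis attached to that model is: "We hypothesize stores in Minneapolis will show no baseline differences and have significantly larger positive slopes for healthy food availability outcomes over time". No knot, step or curved term is mentioned, and the coding of time is not given.

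On the timing of the effect, the same section expects Minneapolis stores to have "higher healthy food availability scores at all 3 time points" and names "immediate compliers, delayed compliers, non-compliers" as possible subgroups. Section III, Aim 1, expects that "differences in intervention vs. control stores will continue to increase over 24 months".

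The section also plans a repeated measures model with time as a four-level factor. Its 3 df Time x Condition interaction is the overall test, followed by single-df contrasts that adjust for baseline differences. The Aim 1 text presents the growth curve as a supplement to this. The opening paragraph of the section names both models as tests of the primary hypothesis.

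**The concern.** Three of the four points that fix each store's line come after the policy. If the ordinance lifts Minneapolis scores by month 4 and the gain then flattens, the best straight line starts above the true baseline and rises too gently. The fitted intercepts then differ between cities even when the baseline scores did not. The error is largest when the policy works at once.

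Stores are not randomised, there is one comparison city, and there is one pre-policy wave. A reported baseline advantage for Minneapolis would naturally be read as pre-existing confounding. It could also contradict the baseline estimate from the categorical-time model, and the plan does not say which of the two governs.

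**Working it through.** **Inputs from the plan (section VI, Sample Size Considerations).** 208 stores; two-sided alpha 0.05; power 0.80; detectable difference 2.2 points, about 0.4 SD, hence SD = 2.2/0.4 = 5.5; benchmark effect 4 points; 20% attrition.

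**Assumptions not in the plan.** 1:1 split between cities, equal within-store correlation rho = 0.6 (varied below), complete data, no covariates, true baseline difference 0.

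**1. The plan's own figure.** (1.960 + 0.842) x 5.5 x sqrt(4/208) = 2.14 points. With 20% attrition (166.4 stores) it is 2.39. The plan states about 2.2 and 2.4, so the scale is reproduced.

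**2. Intercept under a step.** Let the city difference be 0, d, d, d, with the baseline wave as time zero. The least-squares intercept is d x (0.75 − tbar²/SS), where tbar is the mean time and SS the sum of squares of time about it.
- Months 0, 4, 12, 24: tbar = 10, SS = 336; 0.75 − 100/336 = 0.452. The slope is 10/336 = 0.0298d per month, a fitted 24-month rise of 0.714d instead of d.
- Waves coded 0 to 3: tbar = 1.5, SS = 5; 0.75 − 2.25/5 = 0.30.
- Elapsed time with baseline 7 months before the policy (0, 11, 19, 31): tbar = 15.25, SS = 512.75; 0.75 − 0.454 = 0.296. Baseline at 3 or 5 months before gives 0.377 or 0.334. Study Timeline has baseline work running from September 2014 to early 2015 and the policy starting in April 2015, so these gaps are plausible.

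For d = 4 the false baseline difference is 4 x 0.296 = 1.2 to 4 x 0.452 = 1.8 points.

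**3. False rejection.** The SE of the intercept difference is sqrt(4/208 x 5.5² x [rho + (1 − rho)(1/4 + tbar²/SS)]).
- Months 0, 4, 12, 24: the bracket is 0.6 + 0.4 x 0.548 = 0.819; SE = 0.69; 1.81/0.69 = 2.62; rejection 75%.
- Baseline at −7 months: the bracket is 0.6 + 0.4 x 0.704 = 0.881; SE = 0.72; 1.19/0.72 = 1.66; rejection 38%.
- For d = 2.2 the range is 15% to 30%.
- Varying rho from 0.3 to 0.8 at d = 4 gives 82% to 70% with months coding and 43% to 37% with wave coding.

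A simulation of 150 mixed-model fits (months coding, rho 0.5, d = 4) gave a mean intercept difference of 1.91 and 82% rejection (formula: 1.81 and 77%). With baseline estimated freely, the simulated mean was 0.06 points with 6.7% rejection.

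**4. Effects that keep growing.** Here d is the 24-month effect, with rho 0.6.

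| Share of d at 4/12/24 months | Baseline at | Share in intercept | Rejection, d = 4 |
|---|---|---|---|
| 50/75/100% | 0 | 0.19 | 20% |
| 50/75/100% | −3 months | 0.13 | 12% |
| 50/75/100% | −5 months | 0.10 | 9% |
| 50/75/100% | −7 months | 0.07 | 7% |
| 33/67/100% | −3 to −5 months | 0.05 to 0.02 | 5% to 6% |
| linear in months | 0 | 0 | 5% |

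**The case against.** The strongest reply is that the plan already estimates baseline without this constraint. The categorical-time model is the overall test, and its contrasts compare change from baseline, which does not require equal baselines. That stands. A reader might infer that the main Aim 1 test is biased; the documents do not support this, because that model draws no line through the waves.

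A reader might also infer that the plan decides comparability of the cities from the fitted intercept. It does not say so. It states a hypothesis about the growth curve, gives no decision rule, and handles non-randomisation through covariates and baseline-adjusted contrasts. What remains is a prespecified statement about baseline that the chosen model can get wrong.

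Third, a pure step is not the shape hypothesised in Specific Aims, where the gap keeps widening, and step 4 shows much smaller errors for such shapes. This also stands. The 38% to 75% range is the extreme case, and its top end needs the baseline wave coded as month 0 relative to the policy. The plan nevertheless expects an effect at every follow-up and allows for immediate compliers, so front-loading lies within its own expectations.

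Finally, the slope hypothesis would usually survive. Under a pure step, with rho 0.6 and no random-slope variance, power for the slope difference is at least 99.5% at d = 4 and 70% to 87% at d = 2.2. The slope understates a step, but it would seldom be missed at the benchmark effect.

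**Conclusion.** The point holds for the supplementary growth curve and only when the effect is front-loaded. The distortion ranges from substantial (a full step by month 4) to negligible (growth close to linear). The intercept shares depend only on the effect shape and the time coding. The rejection rates also rest on the assumed 1:1 split, the correlation, and an SD back-calculated from rounded figures; the 4-point benchmark comes from a different policy, and the plan does not give its time course. It would be too strong to say that the error disappears only under exactly linear growth, since moderately front-loaded effects that go on growing also give small errors. This is a weakness in one secondary statement about baseline, worth correcting because the correction is cheap.

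**What to change.** - Take the baseline city comparison from the observed baseline wave or the categorical-time model, with its 95% CI, and state that the growth-curve intercept is not used for it.
- State how time is coded and which wave or date is time zero.
- Add to the growth curve a fixed post-policy step and a step x Condition term, alongside a slope over 4 to 24 months and its Condition term. Do not require a step that varies by store: with four waves it could add up to three variance and covariance parameters.

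Under a step effect the expected baseline difference then returns to 0. Data and software are unchanged. The cost is two more fixed parameters and a less precise slope. As a guide, the slope over months 4, 12 and 24 has SS = 87.1 + 1.8 + 113.8 = 202.7 against 336 for the single line, so its SE grows by a factor of sqrt(336/202.7) = 1.29. The observed baseline comparison has SE 5.5 x sqrt(4/208) = 0.76, slightly wider than the 0.69 to 0.72 of the fitted intercept.

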We will test Aims 2 (assess changes in nutritional quality of purchases) and 3 (assess changes in home food availability among households that shop at small and non traditional, urban food stores) using similar models. For Aim 2, the data are repeated cross-sections (rather than true panel or longitudinal data) of small store consumers. Although individual change cannot be examined, we will assess aggregate change attributable to the policy change. Each nutritional quality measure (i.e., energy density, calories) will be regressed on Time, Condition, and the Time x Condition interaction, as well as a number of individual-level covariates. We hypothesize that the interaction will be significant, with purchases made in Minneapolis stores showing significantly lower energy density and calories at 4-, 12-, and 24-months post policy. For Aim 3, the data are true longitudinal data of households that frequently shop at small and non-traditional, urban food stores. This uses an identical repeated measures model as Aim 1, now with household as the unit of analysis. We will regress each food availability outcome variable separately on Time, Condition, and the Time x Condition interaction, as well as a number of household-level covariates. We hypothesize that the interaction will be significant, with households in Minneapolis showing significantly higher availability of healthy food and significantly lower availability of unhealthy food at 4-, 12-, and 24months post policy.

Analyses will be conducted with SAS or MPlus^(35, 36) Covariance pattern and growth curve models will be estimated using the SAS v9.3 MIXED procedure, which can estimate a large number of models, including general linear mixed models designed to analyze repeated measures and multilevel change. This procedure has built-in statements for specific planned contrasts. Growth mixture models will be estimated using MPlus v7.⁽³⁶⁾

Sample Size Considerations

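### Aim 2's 50-calorie detectable difference cannot be checked as stated, and fits the planned Time x Condition tests only if the calorie SD is at most about 110 to 156 kcal, when it would not be very small in SD units

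*Combined protocol and SAP*

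**What the plan says.** The Aim 2 sample size sentence reads: "424 intercept surveys at four rounds will allow us to detect a 50-calorie difference (a very small effect size) between conditions over time". Alpha is 0.05 two-sided and power 0.80. Section IV (Study Population) confirms that 424 is the number of customers at each time point. The variance is taken from reference 28 and no value is printed. The customer split between Minneapolis and St. Paul, the contrast powered and any allowance for customers sharing a store are not given either.

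For Aim 1, the same paragraph does put its detectable difference on a standardised scale: "This is approximately 0.4 SD units".

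Section VI (Analyses That Will Be Performed) defines the test: "The overall test of any difference by policy condition over time is the Time x Condition interaction, a 3 degree of freedom test". Single-df contrasts at 4, 12 and 24 months follow. Aim 2 uses a similar model, with covariates ("as well as a number of individual-level covariates"). Its hypothesis is about the interaction: "We hypothesize that the interaction will be significant, with purchases made in Minneapolis stores showing significantly lower energy density and calories". On the data structure: "For Aim 2, the data are repeated cross-sections (rather than true panel or longitudinal data) of small store consumers". Section III frames the Aim 2 hypothesis as "controlling for any baseline differences, energy density and calories purchased in Minneapolis stores" being lower than in St. Paul at each follow-up.

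**The concern.** The planned test compares the change from baseline between two cities, using different customers at each round. Such a difference of differences has twice the variance of a one-round city comparison, and with repeated cross-sections no within-person correlation offsets this. It is therefore surprising that 424 surveys per round should give 80% power for a very small effect. Among the analyses tried below, the only ones that detect less than 0.2 SD pool rounds and make no contrast with baseline.

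The SD also comes from a source whose title in the bibliography concerns snacking in children, whereas intercept customers must be 18 or older. The documents do not show whether that makes the SD too small or too large.

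Calories purchased is in the study title and in Aim 2's primary hypothesis. A reader who takes the sentence at face value could read a null calorie result as excluding even very small differences. The planned test may not support that.

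**Working it through.** **Inputs from the plan.** 424 customers per round, four rounds, two-sided alpha 0.05, power 0.80, Time x Condition interaction with 3 df plus single-df contrasts.

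**Assumed, because not stated.** Equal city split (212 per city per round), independent customers, no variance explained by covariates. Effects are in SD units. 0.2 SD is used as the conventional benchmark for a small standardised mean difference; the plan sets none.

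**The plan's own figures.** The Aim 1 figure reproduces. With 104 stores per city, (1.960 + 0.842) x sqrt(2/104) = 2.8016 x 0.1387 = 0.389 SD, matching the stated 0.4 SD as a two-group comparison at one time point. The Aim 2 figure can be neither reproduced nor refuted in calories, because no SD is given.

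**Single-df contrast, follow-up minus baseline.** The variance of the difference of differences is 4/212, so the detectable effect is 2.8016 x sqrt(4/212) = 0.385 SD. For this to equal 50 kcal, the SD must be 50/0.385 = 130 kcal.

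**3 df interaction.** Noncentrality = (212/2) x S x d², where d is the largest city difference in change and S is the sum of squared deviations of the effect pattern from its mean over the four rounds. Denominator df = 1,696 - 8 = 1,688. Power of 80% needs noncentrality 10.93, so d = sqrt(10.93/(106 x S)). The last column gives power if d is 0.2 SD.

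| Effect at 0, 4, 12, 24 months | S | Detectable d (SD) | Largest SD for 50 kcal | Power at 0.2 SD |
|---|---|---|---|---|
| 0, 0, d, d (delayed) | 1.000 | 0.321 | 156 | 38% |
| 0, d, d, d (constant) | 0.750 | 0.371 | 135 | 29% |
| 0, d/6, d/2, d (linear in months) | 0.583 | 0.420 | 119 | 23% |
| 0, d/3, 2d/3, d (linear by round) | 0.556 | 0.431 | 116 | 22% |
| 0, d/2, d/2, d | 0.500 | 0.454 | 110 | 20% |

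The plan names no pattern for Aim 2. For Aim 1 it expects that "differences in intervention vs. control stores will continue to increase over 24 months", which resembles the linear rows. Delayed compliance is also anticipated for some stores.

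**Contrast power at 0.2 SD.** 0.2/sqrt(4/212) = 1.456, and 1.456 - 1.960 = -0.504, giving about 31%.

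**Power for 50 kcal at assumed SDs (contrast / 3 df with constant effect).** 100 kcal: 95% / 97%. 130: 80% / 83%. 200: 44% / 44%. 250: 31% / 29%. 300: 23% / 21%. The documents support no particular row.

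**Comparisons that ignore baseline.** One round: 2.8016 x sqrt(2/212) = 0.272 SD. Three post-policy rounds pooled: 2.8016 x sqrt(2/636) = 0.157 SD. Four rounds pooled: 2.8016 x sqrt(2/848) = 0.136 SD. None of these is the planned test.

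**Sensitivity of the contrast (0.385 SD).** Covariates explaining 20% of variance: 0.385 x sqrt(0.8) = 0.344. City split 60:40: 0.393. Clustering design effect 1.2: 0.385 x sqrt(1.2) = 0.422. To reach 0.2 SD, covariates would have to explain 1 - (0.2/0.385)² = 73% of the variance. The same formula gives 61% to 81% for the 3 df patterns above.

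**The case against.** The strongest reply is that the label need not be a standardised mean difference. For a 3 df F test, Cohen's f is a usual measure. Here f = sqrt(10.93/1,696) = 0.080, below the conventional small value of 0.10. On that metric the label fits the planned test. The label may also describe the raw calorie amount. The same paragraph calls the Aim 3 effects small with 68 households, where an equal two-group comparison detects 2.8016 x sqrt(2/34) = 0.68 SD before attrition, so the labels may not be on the SD scale at all. All of this stands: the mismatch depends on reading the label as a mean difference in SD units. That is still the natural reading of words attached to a calorie difference, in a paragraph that reports Aim 1 in SD units.

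A reader might go further and infer that 50 calories is miscalculated, or that Aim 2 is underpowered. The documents support neither. With an SD of 100 kcal, the planned contrast would have 95% power for 50 kcal. Nor do they show that the child-based variance flatters the figure; it could err either way.

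The plan says that multiple rounds and covariates will make detectable effects much smaller, but it says so for Aim 1, where the same stores are measured repeatedly. Aim 2 covariates could help, though the share of variance needed to reach 0.2 SD is large. Within-store clustering, if positive, or an uneven city split would work the other way.

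Finally, the plan is dated December 2017 and the last round was due to begin in April 2017, so no design decision turns on this sentence. That lowers the severity but leaves the stated sensitivity uncheckable.

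**Conclusion.** The point holds as a question of fit and checkability. Under an equal city split, independent customers and no covariate gain, the planned Aim 2 tests have 80% power for about 0.385 SD per contrast and 0.32 to 0.45 SD for the 3 df interaction (0.37 SD for a constant effect). So either the calorie SD is at most about 110 to 156 kcal, and 50 kcal is then not very small in SD units, or the difference is very small in SD units and power for the planned tests falls well short of 80%. Which of these applies cannot be told, because the SD is not stated. Severity is minor to should-fix: a reported sensitivity figure needs restating, and the planned test itself is not at fault.

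**What to change.** Recompute the Aim 2 detectable difference for the tests actually planned, and report it in kcal and in SD units:

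- for each baseline-to-follow-up contrast, x = 2.80 x SD x sqrt(2 x (1/n1 + 1/n2) x DE x (1 - R²)), where n1 and n2 are the actual Minneapolis and St. Paul counts per round (the formula takes them as the same in both rounds), DE is the design effect for customers within stores, and R² is the share of variance explained by covariates;
- for the 3 df interaction, the same inputs under a named effect pattern.

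Take the SD from adult purchases in the study's own baseline intercept survey and print it, with the values used for DE and R². Delete the effect-size label or name its metric; if a raw calorie amount is meant, say so.

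The cost is one recalculation and a few sentences. The stated figure may become less favourable. Enrolment and the planned analysis do not change.
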